# Objectives

# **Primary objective**

• To describe the antidepressive effectiveness of agomelatine in patients with depression episode occurred after COVID-19 assessed by HAMD-17 after 8 weeks of treatment in the daily clinical practice.

## Secondary objectives

- To describe effectiveness of agomelatine on anxiety symptoms associated with the depression and assessed by HAMD-17 (point 10 and 11) after 8 weeks of treatment of patients included in the study.
- To describe effectiveness of agomelatine on global improvement and social functioning assessed by CGI score after 8 weeks of treatment of patients included in the study.
- To describe effectiveness of agomelatine on quality of life in patients with depression episode occurred after COVID-19 assessed by SF-36 questionnaire after 8 weeks of treatment of patients included in the study.
- To describe tolerability of agomelatine after 8 weeks of treatment based on rate of adverse events leading to drug discontinuation in patients included in the study.

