#### Data collection at the Final Visit (V3 - week 8):

- HAMD-17 score.
- CGI-Improvement score.
- Presence of exclusion criteria.
- Concomitant current use of other medications.
- Quality of life assessment (SF-36).
- Adverse events/drug reactions/special situations.
- Change in therapy with agomelatine if occurred or required.

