#### Scoring:

The SF-36 has eight scaled scores; the scores are weighted sums of the questions in each section. Scores range from 0 - 100 Lower scores = more disability, higher scores = less disability Sections:

- Vitality
- Physical functioning
- Bodily pain
- · General health perceptions
- · Physical role functioning
- Emotional role functioning
- Social role functioning
- Mental health

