# Appendix 3.

At ASSE and W0 visits, the global improvement (CGI-I) is not assessed.								
Cross the appropriate box.								
1. Severity of illness		2. Global improvement						
Considering your total experience with this particular population, how ill is the patient at this time?		Rate total improvement whether or not, in your judgement, it is due entirely to drug treatment. Compared to his condition at the inclusion visit how much has he changed?						
0	Not assessed	0 🗆	Not assessed					
□ 1	Normal, not at all ill	□ 1	Very much improved					
□ 2	Borderline mentally ill	□ 2	2 Much improved					
□ 3	Mildly ill	□ 3	Minimally improved					
□ 4	Moderately ill	□ 4	No change					
□ 5	Markedly ill	□ 5	Minimally worse					
□ 6	Severely ill	□ 6	Much worse					
□ 7	Among the most extremely ill patients	□ 7	Very much worse					

IC4-20098-069- RUSPlease send this form immediately by [contact] or by email to [contact], or pass to the associate of the company.								
Year of birth or Age Gend	er l	Height	Weight	Patient's ID	):			
or   N	ſ/F  _				_ _ _			
Description of adverse even	nt/reaction/spe	ecial situat	ion:	Date of ev	vent onset	Date of event   termination (in case   of recovery)		
Criteria of seriousness: DO YES (please, spec Death Hospitalization or Persistent or signi Congenital anoma Medically significa	Outcome:       Recovered       Recovered with consequences (persistent structural or functional impairment)       Not recovered       No recovered       Death       Unknown							
General disease(s) / Concomitant disease(s) (please indicate year when first diagnosed).								
Course adverse event/reaction/special situation (please enclose relevant findings, e.g. laboratory, hospital reports, histology, etc.):								
Causal relationship with intake of studied drug:       NO     YES     NOT APPLICABLE       If «Yes», please indicate dates of the use of studied drug in the first line of the table below:     If end to the use of studied drug in the first line of the table below:       If «No» or «Not applicable», please specify whether the adverse event/special situation is related to the medication of Servier company (which is specified in the table below):       NO     YES Please indicate the name of the medication of Servier company:								
List of current medications	Daily dose / route of administration	from	Dates of inta t	ke: o	Indication			
			-					
			-					
			-					

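### Social functioning is a secondary objective assigned to the CGI, which has no social item, and none of the nine secondary variables isolates it

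*Combined protocol and SAP*

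**What the plan says.** The Secondary objectives section of the combined protocol and SAP includes: "To describe effectiveness of agomelatine on global improvement and social functioning assessed by CGI score after 8 weeks of treatment". A separate objective in the same list covers quality of life and is tied to the SF-36.

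Appendix 3 reproduces the CGI. Item 1 asks "how ill is the patient at this time". Item 2 instructs the rater: "Rate total improvement whether or not, in your judgement, it is due entirely to drug treatment". The form notes: "At ASSE and W0 visits, the global improvement (CGI-I) is not assessed". Table 1 and the visit lists for weeks 2, 4 and 8 schedule only the "CGI-Improvement score".

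The Secondary variables section has one CGI entry, item 2, and three SF-36 entries: total, physical component and psychiatric component. Appendix 2 lists eight SF-36 scales, one of which is "Social role functioning", and gives the scoring direction: "Scores range from 0 - 100 Lower scores = more disability, higher scores = less disability". The SF-36 is completed at all four visits.

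**The concern.** The objective names two concepts, global improvement and social functioning, and gives both to one instrument. Only the first has a matching item and a matching variable. Followed as written, the plan would either leave the social half unreported or present the CGI improvement rating as evidence on something it does not ask about. If the gap is noticed only at analysis, the choice of a substitute measure would be made with the data in hand. A suitable scale is already being collected, so the loss is avoidable.

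**Working it through.** The plan gives no figure for social functioning. Its only computed design figure is the sample size for the primary variable. That reproduces: a one-sample t-test with difference 3.0, SD 3.8 and one-sided alpha 0.005 gives power 0.90991 at n = 28, and 28 / (1 − 0.30) = 40. The present point does not depend on it.

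**1. CGI content (Appendix 3).** There are two rated items, severity and global improvement. Items with social content: 0 of 2.

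**2. Secondary variables.**

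| # | Variable | Isolates social functioning? |
|---|---|---|
| 1 | HAMD-17 response | No |
| 2 | HAMD-17 remission | No |
| 3 | HAMD-17 item 10 | No |
| 4 | HAMD-17 item 11 | No |
| 5 | CGI item 2 | No |
| 6 | SF-36 total | No, mixed domains |
| 7 | SF-36 physical component | No, mixed domains |
| 8 | SF-36 psychiatric component | No, mixed domains |
| 9 | Adverse events or reactions leading to discontinuation | No |

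Count: 0 of 9.

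**3. Share of the SF-36.** Items printed in Appendix 2, questions 1 to 11: 1 + 1 + 10 + 4 + 3 + 1 + 1 + 1 + 9 + 1 + 4 = 36. Only questions 6 and 10 ask about social activities, so the social content is 2 of 36 items and 1 of 8 scales. A total or component score cannot stand in for it.

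**4. Timing.** Questions 6 and 10 use a 4-week recall. The baseline form covers weeks −4 to 0, and the week-8 form covers weeks 8 − 4 = 4 to 8, so the two windows do not overlap. The week-2 form covers weeks 2 − 4 = −2 to 2 and so reaches back before inclusion. Week 8 is therefore the right time point, and it is the one the objective names.

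**5. Precision of the missing variable.** Evaluable n = 100 × (1 − 0.30) = 70, using the planned minimum number of patients and the full dropout allowance from the Statistical analysis section. The documents give no SD for change in this scale, so 15 to 30 points is an assumption. SE = SD / √70, and the 95% half-width is t(69) × SE with t = 1.995.

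| Assumed SD of change | SE | 95% half-width |
|---|---|---|
| 15 | 1.79 | 3.58 |
| 20 | 2.39 | 4.77 |
| 30 | 3.59 | 7.15 |

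**6. Two minor wording points.** The CGI variable is labelled a mean change, but item 2 is itself a rating of change since inclusion and has no baseline value. The line most naturally means the observed rating at each visit. Separately, Appendix 2 describes eight scale scores but no total, and names no algorithm for the total or the two components listed as variables.

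**The case against.** The best defence is that little turns on this. The objective is secondary and descriptive, no test or decision changes, and deleting the reference to social functioning would also remove the mismatch. That is true and limits the weight of the point, but deletion would discard an answer the study already collects.

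It can also be said that social functioning is not wholly absent. A global rating need not exclude it, the SF-36 total takes in the social items, and the Biometrics section promises descriptive statistics for all indicators. None of this supplies an endpoint. The objective itself separates social functioning from global improvement, the SF-36 summary scores mix domains, and the Biometrics section names no SF-36 scale. Reporting the social scale is not forbidden, but it is not pre-specified.

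The Appendix 3 form also prints boxes for severity, so it is not certain that only the improvement item will be recorded. This does not help, because the severity item has no social content either.

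Two technical remarks stand. Appendix 2 does not say which questions form each scale, so assigning questions 6 and 10 to the social scale is an inference from their wording. Those two questions are also printed in opposite directions (1 is the best answer to question 6 and the worst to question 10), so recoding is needed to meet the stated 0–100 direction. Finally, the precision figures are illustrative; the mismatch does not depend on them.

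**Conclusion.** The concern holds. Social functioning is a stated objective with 0 of 2 CGI items and 0 of 9 secondary variables to answer it. The consequence is limited to half of one secondary descriptive objective. The primary variable, sample size, HAMD-17 secondary variables and quality-of-life objective are unaffected. It should still be corrected, because the plan as written would answer a stated objective from an instrument that does not measure it.

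The counts rest on the forms and lists as printed. A short part of the appendices after the CGI form was not available for this check. A further CGI item there is unlikely, and in any case the Secondary variables section uses item 2 only. The precision range rests on the assumed SD and on 70 evaluable patients.

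**What to change.** 1. Take social functioning out of the CGI objective and place it under the SF-36 objective.
2. Add one secondary variable: mean change from baseline to week 8 in the SF-36 social scale (questions 6 and 10), recoded to a common direction and scored 0–100 with higher scores meaning less disability, as Appendix 2 states.

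Minor clarifications to make at the same time:

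- Describe the CGI variable as the observed improvement rating at weeks 2, 4 and 8, with code 0 (not assessed) treated as missing.
- Name the SF-36 scoring algorithm for the scales, for the two components and for any total that is kept, including which questions feed each scale.

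The cost is one reworded objective, one added variable and one more descriptive table. No new data, visits or forms are needed, since the SF-36 is already completed at baseline and week 8.

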## Study variables

## **Primary variables:**

• Mean change from baseline (BL) in total HAMD-17 score assessed at week 8 of the observational period.

#### Secondary variables:

- % of patients defined as responders to the treatment (HAMD-17 total score decrease ≥ 50%) at week 8 of the observational period.
- % of patients achieving disease remission (defined as HAMD-17 total score < 7) at week 8 of the observational period.
- Mean change from BL in HAMD-17 point 10 "psychological anxiety" assessed at week 8 of the observational period.
- Mean change from BL in HAMD-17 point 11 "somatic anxiety" assessed at week 8 of the observational period.
- Mean change in scores of the Clinical Global Impression scale (CGI), item 2 (global improvement) at W2,W4,W8 assessed at week 8 of the observational period.
- Mean change from BL in total score of the SF-36 QoL questionnaire reported by patients at week 8 of the observational period.
- Mean change from BL in score of the SF-36 QoL questionnaire (physical component) reported by patients at week 8 of the observational period.
- Mean change from BL in score of the SF-36 QoL questionnaire (psychiatric component) reported by patients at week 8 of the observational period.

• Number of adverse events/ adverse drug reactions leading to drug discontinuation during the observational period.

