# Selection of the study population

# **Inclusion criteria**

- 1. Obtained signed informed consent from the patient.
- 2. Age of 18-65 years old.

- 3. Out-patient with confirmed COVID 19 infection within 3 months period before the date of inclusion.
- 4. Confirmed depression with total HAMD-17 score of 8-24 required treatment with antidepressive medicines.
- 5. Decision to administer agomelatine preceeds the decision to include a patient in the study.

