## The scheme of TELESPHOR study

#### Statistical analysis

Due to non-interventional nature of the study design descriptive statistical methods will be used. Search statistical analysis will be performed in the following groups of patients: in the clinical study the primary end point of the study is a mean change from BL in HAMD-17 total score assessed at week 8 of the observational period.

In the article of O.V. Vorob'eva "Valdoxan in the Treatment of Depression in Neurological Practice: Results of the Russian Multicenter Naturalistic Study "Resonance" from Zhurnal Nevrologii i Psikhiatrii imeni S. S. Korsakova, Vol. 112, No. 9, Iss. I, pp. 47—51, September, 2012, was described the efficacy and tolerance of Valdoxan (agomelatine) in mild and moderate depression due to neurological diseases. Treatment efficacy was evaluated using standard psychometric tools, one of them was the 17-point Hamilton depression scale (HAMD-17).

The mean total score on the HAMD-17 was  $15.3 \pm 3.8$  points. Significant decreases in total points scores on the HAMD-17 were seen by the end of the first week of treatment. After completion of treatment courses (at six weeks of treatment), the mean score was  $4.7 \pm 3.2$  points. At six weeks of treatment, responders (patients with total HAMD-17 scores which decreased at least twofold) constituted 82.33% of all patients treated.

The following general assumptions were made for the sample size calculations:

1) One-sided (directional) statistical hypothesis for mean:

H0:  $m1 - m0 \le 0$ HA:  $m1 - m0 \ge 0$ 

where m1 stands for sample (study) mean of the corresponding variable (change from BL in HADS total score assessed at week 8 of the observational period), and m0 stands for the population mean (constant).

2) Possible standard deviation is 3.8 points

- 3) Planned study power is 90%, accordingly, type II ( $\beta$ ) error is 0.1
- Overall significance level is 0.01 that corresponds to two-sided type I (α) error of 0.01 or one-sided type I (α) error of 0.005
- 5) Dropout during the study period to 30%.

Calculations for each of the parameters listed above were performed using the validated PASS sample size calculation software, with main outputs (screenshots) provided under the assumptions summarized above.

Numeric Results Hypotheses: H0: μ ≤ μ0 vs. H1: μ > μ0									
_		_		Diff		Effect		_	
Power	N	μ0	μ1	μ1 - μ0	σ	Size	Alpha	Beta	
		0	0,0	0,0	3,8	0,00000	0,005		
0,90031	861	0	0,5	0,5	3,8	0,13158	0,005	0,09969	

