#### **One-Sample T-Tests**

#### References

Zar, Jerrold H. 1984. Biostatistical Analysis (Second Edition). Prentice-Hall. Englewood Cliffs, New Jersey.

As can be seen from the various scenarios provided depending on the planned difference, approximately 28 study subjects will be enough to detect at least a 3.0-point difference between the sample and population means with 90% power at 0.005 one-sided significance level. Dropout-Inflated Enrollment Sample Size is 40 study subjects.

Despite that sample size calculation is 40 patients, at least 100 patients with MDD will be invited to participate in the study.

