# Assessment of the severity of condition using Hamilton Depression Rating Scale:

- 0-7 «normal» (no marked symptoms of anxiety and depression)
- 8-15 «mild depression»
- 16-24 «moderate depression»
- 25 and more «severe depression»

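### Should remission at week 8 be HAMD-17 ≤ 7 instead of < 7, to match the 0-7 normal band on the study's own rating form?

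*Combined protocol and SAP*

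**What the plan says.** Three places in the combined protocol and SAP bear on the point.

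- **Secondary variables.** One item is the percentage "of patients achieving disease remission (defined as HAMD-17 total score < 7) at week 8 of the observational period". The HAMD-17 total is a whole number, so remission means 0 to 6. This is the only definition of remission in the document.
- **Appendix 1, severity assessment.** The key reads "0-7 «normal» (no marked symptoms of anxiety and depression") for the lowest band and "8-15 «mild depression" for the next. It grades severity and does not mention remission.
- **Inclusion criteria, criterion 4.** "Confirmed depression with total HAMD-17 score of 8-24 required treatment with antidepressive medicines". The entry floor of 8 agrees with the Appendix 1 key.

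The Biometrics section plans descriptive statistics only, with absolute and percentage frequencies for categorical variables, calculated among patients with data. Table 1 schedules the HAMD-17 at every visit.

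**The concern.** Two of the three places draw the line between 7 and 8, while the remission rule draws it between 6 and 7. Exactly one score falls between the two lines. A patient with a week-8 total of 7 is in the form's normal band and could not have entered the study with that score, yet is not counted as remitted. If that patient started at 14 or more, the same visit also makes them a responder, since (14 − 7)/14 = 50%. It is natural to suspect that < was typed for ≤.

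The study has one arm and no comparator, so a shift in the cut-off does not cancel between groups. The reported percentage is itself the result. A reader who applied the printed key to the same totals would get a different figure whenever at least one patient scored exactly 7, and the protocol would not explain why.

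**Working it through.** **The cut-offs side by side.** Normal band {0,…,7}; depression {8 and above}; remission {0,…,6}. The only total that is neither in a depression band nor in remission is 7. So the rate under ≤ 7 exceeds the rate under < 7 by exactly the share of patients scoring 7, and can never be lower.

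**Does any plan figure depend on the cut-off?** The plan gives no expected remission rate. Its sample size rests on the mean change in score: one-sample t-test, difference 3.0, SD 3.8, one-sided α 0.005. Recomputing with the noncentral t gives N = 28 with power 0.90991, as printed, and 28/(1 − 0.30) = 40, also as printed. The remission cut-off does not enter.

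**How large could the share at 7 be?** The only end-of-treatment distribution in the document is in the Statistical analysis section: "After completion of treatment courses (at six weeks of treatment), the mean score was" 4.7 ± 3.2, in a cited study of agomelatine "in mild and moderate depression due to neurological diseases". Using it for week 8 after COVID-19 is an assumption, and so is the shape of the distribution.

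With a normal distribution and continuity correction:

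- P(≤ 6) = Φ((6.5 − 4.7)/3.2) = Φ(0.5625) = 0.713
- P(≤ 7) = Φ((7.5 − 4.7)/3.2) = Φ(0.875) = 0.809
- Share at 7 = 0.809 − 0.713 = 0.096

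The negative binomial with the same mean and variance has p = 4.7/3.2² = 0.459 and r = 4.7²/(3.2² − 4.7) = 3.99.

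The number of evaluable patients uses the planned "at least 100 patients with MDD will be invited to participate in the study" and the assumption "Dropout during the study period to 30" per cent: 100 × (1 − 0.30) = 70.

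| Assumed shape (mean 4.7, SD 3.2) | < 7 | ≤ 7 | Gap (points) | Of 70 patients |
|---|---|---|---|---|
| Normal, continuity-corrected | 71.3% | 80.9% | 9.6 | 6.7 |
| Same, cut off below zero (moments not rematched) | 69.7% | 79.9% | 10.1 | 7.1 |
| Discretised normal on 0-52, mean and SD rematched | 72.5% | 80.7% | 8.1 | 5.7 |
| Negative binomial | 75.4% | 82.6% | 7.2 | 5.0 |

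**Wider range.** With means of 4 to 8 and SDs of 3.2 to 5, the gap runs from 6.7 to 12.4 points (normal) and from 3.8 to 12.7 points (negative binomial). That is about 3 to 9 of 70 patients.

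**Scale.** The 95% half-width of a rate of 71.3% in 70 patients is 1.96 × √(0.713 × 0.287/70) = 0.106; at 75.4% it is 0.101. The shift is comparable to or smaller than the sampling margin. That is context only, because a shift in definition is not random error.

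**What ≤ 7 would cost.** A patient who enters at 8 would count as remitted after a drop of 1 point, against 2 points under < 7. If the cited baseline (15.3 ± 3.8) is assumed and restricted to 8-24, the share entering at 8 is [Φ(−1.79) − Φ(−2.05)]/[Φ(2.42) − Φ(−2.05)] = 0.017, about 1 of 70 patients.

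**The case for a change.** The best argument for a change is that the protocol's own form and its entry criterion agree on where depression begins, that only the remission rule departs from them, and that the departure could move a headline secondary percentage by several points in a study with no control group. The totals are collected anyway, so aligning the definition, or adding a second row, would cost one line of text and one table row.

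The facts in that argument stand: the cut-offs differ, no reason is given, and the effect on the rate may not be trivial. The inference does not follow. A severity band and a remission rule serve different purposes, and no section says that remission must equal the normal band. The band is described as lacking *marked* symptoms, which leaves room for a stricter notion of remission. The absence of a stated reason is not peculiar to this cut-off either, since the 50% responder rule in the same list has none.

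Nor does alignment improve the result. A move to ≤ 7 can only raise the rate, and in a single-arm study that is a change in the sponsor's favour to a definition already fixed. An explanatory sentence would be a courtesy to the reader and would alter no number. An extra ≤ 7 row would correct no stated result. Biometrics already foresees frequency distribution tables for composite indicators; it does not say whether HAMD-17 totals are among them, but the totals will be in the database if anyone wants the other share.

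**Conclusion.** The remission cut-off is one point stricter than the normal band in Appendix 1 and the entry floor, and the plan does not say why. That is a missing explanation for a clear definition. Followed as written, the plan yields a reproducible percentage whose meaning is plain from its label, HAMD-17 below 7. Any error in comparison with the ≤ 7 share has a known direction: the planned rate is the lower or equal one.

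The gap is about 7 to 10 percentage points if the cited week-6 mean and SD carry over, and about 4 to 13 points over the wider assumed range. These figures are illustrative, because they borrow from another population at another time point and assume a distribution shape. The conclusion does not depend on them. It rests on there being one remission rule, no competing rule, and no loss in keeping the conservative one. Only one descriptive secondary variable is involved, with no hypothesis or decision attached to it. No change to the plan follows.
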